1.2. Study Objectives

1.2.1. Primary Objective

To assess whether dupilumab as adjunct to AR101 compared to placebo as adjunct to AR101 improves desensitization at the completion of the up-dosing period, defined as an increase in the proportion of subjects who pass a post up-dosing DBPCFC at visit 16

1.2.2. Secondary Objectives

- To assess whether dupilumab as adjunct to AR101 compared to placebo as adjunct to AR101 improves desensitization at the completion of up-dosing, defined as an increase in the cumulative tolerated dose (log transformed) of peanut protein during a post up-dosing DBPCFC at visit 16
- To assess whether dupilumab as (indefinite [continuously]) adjunct to AR101 compared to placebo maintains desensitization, defined as an increase in the proportion of subjects who pass a post maintenance DBPCFC at visit 22
- To assess whether dupilumab as (limited [previously]) adjunct to AR101 compared to placebo maintains desensitization, defined as an increase in the proportion of subjects who pass a post maintenance DBPCFC at visit 22
- To evaluate the safety and tolerability of dupilumab as adjunct to AR101 compared to placebo
- To assess the effect of dupilumab (compared to placebo) as adjunct to AR101 on the change in peanut-specific IgE, IgG, IgG4, peanut-specific IgG4/IgE ratio, and peanut-specific IgG/IgE ratio

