3.2.2. Rationale for Study Design

AR101, with and without dupilumab, will be tested in a 2-arm, double-blind, randomized, parallel-group study in subjects with confirmed peanut allergy. Pediatric subjects will be enrolled as children represent the majority of subjects with peanut allergy and are a greater risk for accidental ingestion of peanut. Dupilumab/placebo treatment for 28 to 40 weeks as an adjunct to 24 to 36 weeks of daily AR101 treatment will be evaluated, followed by maintenance period of 24 weeks of daily AR101 treatment with concomitant dupilumab or placebo. Two treatment groups are required to provide informative controls and minimize bias on clinical endpoints: dupilumab plus AR101 and placebo plus AR101. Subjects will be treated for 28 to 40 weeks with either Q2W subcutaneous (SC) dupilumab or placebo. After the first 4 weeks of pretreatment, subjects will begin a 24 to 36 week up-dosing regimen of daily oral AR101. The study will assess an up-dosing regimen up to a maximum of 300 mg/day over the following 24 to 36 weeks of the study. If the scheduled bi-weekly up-dosing is not possible, the up-dosing period may be extended by up to 12 weeks (optional visits 15a-f) if necessary to accommodate dose reductions and reescalation as well as COVID-19 restrictions of in-clinic visits. Thus, the up-dosing period will end at week 28 to 40 (including 4 weeks pretreatment, 22 to 34 weeks of flexible up-dosing, and at least 2 weeks at the maximum dose).

Subjects who achieve 300 mg daily dose of AR101 for at least 2 weeks at visit 16 (ie, the end of the up-dosing period, week 28 to 40) will enter a 24-week maintenance period. Subjects treated with dupilumab during the up-dosing period and who achieve 300 mg/day AR101 for at least 2 weeks will be re-randomized to 2 groups, AR101 plus dupilumab (indefinite [continuously]) and AR101 plus placebo (limited [previously]); this will allow an assessment of a lasting or limited effect of dupilumab. Subjects treated with placebo during the up-dosing period and who achieve 300 mg daily AR101 for at least 2 weeks will continue to be treated with placebo plus AR101 during the maintenance period.

This design allows for a direct comparison between adjunct dupilumab plus AR101 to placebo plus AR101 during the 28 to 40 week double-blind treatment period. It will also evaluate the effect of dupilumab in maintaining the response to AR101, defined as an increase in the proportion of subjects who pass a DBPCFC.

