1.2.3. Modifications from the Statistical Section in the Final Protocol

Modifications from protocol amendment 4

- Added that the data will be summarized by treatment groups during pre-dosing period of AR101 (4 weeks) separately.
- Revised the secondary objective "To assess the effect of dupilumab (compared to placebo) as adjunct to AR101 on the change in peanut-specific IgE, IgG, IgG4, and peanut-specific IgG4/IgE ratio" as "To assess the effect of dupilumab (compared to placebo) as adjunct to AR101 on the change in peanut-specific IgE, IgG, IgG4, peanut-specific IgG4/IgE ratio and peanut-specific IgG/IgE ratio".
- Removed the last secondary objective "To assess if dupilumab increases the tolerability of AR101 as measured by the daily symptoms (e-diary) during the up-dosing phase" and corresponding secondary endpoints "Proportion of subjects experiencing allergic symptoms by treatment group during the up-dosing phase, mean severity score for each symptom by treatment during up-dosing phase, maximum severity score for each symptom by treatment during up-dosing phase, and difference in mean/median duration of symptoms by treatment group during up-dosing phase, and difference in mean/median duration of symptoms by treatment group during up-dosing phase (all endpoints measured by the daily symptom e-diary)" due to the low compliance of the allergy symptoms entry in eDiary. Instead, the following exploratory endpoints are added:
 - Proportion of days with one or more of any peanut allergy symptoms excluding food challenge test days during the updosing period up to visit 16
 - Proportion of days with one or more severe form of any peanut allergy symptoms (i.e. severity score of 7 or more) excluding food challenge test days during the updosing period up to visit 16

- Proportion of days with one or more symptoms for each symptom category excluding food challenge test days during the updosing period up to visit 16
- The following exploratory endpoints are added as well:
 - Change in the cumulative tolerated dose (log transformed) of peanut protein during a DBPCFC from visit 22 to visit 25
 - Proportion of subjects who "pass" a DBPCFC with 2044 mg (cumulative) peanut protein at visit 25
 - Change from baseline in total FAQLQ score at visit 16, visit 22 and visit 25 for different types of FAQLQ form

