3.1. The Full Analysis Set (FAS)

FAS includes all randomized subjects. Efficacy analyses will be based on the treatment allocated by the IWRS at randomization (as randomized).

The modified full analysis set (mFAS) includes all FAS subjects who undergo bi-weekly in-clinic up-dosing as described/specified in the protocol and undergo the post up-dosing DBPCFC at Visit 16/Week 28 (a window of -7/+30 days).

The mFAS will be considered as primary analysis set for all efficacy endpoints. The FAS will also be done for all efficacy endpoints as supportive analyses.

FAS-maintenance is a subset of FAS and includes subjects in the FAS who achieve 300 mg/day AR101 for at least 2 weeks in the up-dosing phase and re-randomized based on the treatment allocated by the IWRS at visit 16. The FAS-maintenance is the primary analysis set for efficacy analyses at visit 22.

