4.5.2. Secondary Efficacy Variable(s)

The secondary efficacy endpoints are:

• Change in cumulative tolerated dose (log transformed) of peanut protein during a DBPCFC from baseline to visit 16 in subjects treated with dupilumab plus AR101 vs placebo plus AR101

Note: Due to the positive skew for the distribution of the "cumulative amount of peanut protein", a log transformation will be applied to reduce the skewness

- Proportion of subjects treated with dupilumab plus AR101 vs placebo plus AR101 who reach the 300 mg/day dose of AR101 by visit 16
- Time from randomization to the first-time when subjects reach the 300 mg/day dose of AR101 during the treatment phase (up to visit 16)
- Proportion of subjects (continuously) treated with dupilumab plus AR101 vs placebo plus AR101 who "pass" a post maintenance DBPCFC with 2044 mg (cumulative) peanut protein at visit 22
- Change in the cumulative tolerated dose (log transformed) of peanut protein during a DBPCFC from baseline to visit 22 in subjects (continuously) treated with dupilumab plus AR101 vs placebo plus AR101
- Proportion of subject (previously) treated with dupilumab plus AR101 (and re-randomized to placebo plus AR101) vs placebo plus AR101 who "pass" a post maintenance DBPCFC with 2044 mg (cumulative) peanut protein at visit 22
- Change in the cumulative tolerated dose (log transformed) of peanut protein during a DBPCFC from baseline to visit 22 in subjects (previously) treated with dupilumab plus AR101 (and re-randomized to placebo plus AR101) vs placebo plus AR101
- Percent change from baseline to visit 16 in peanut-specific IgE in subjects treated with dupilumab plus AR101 vs subjects treated with placebo plus AR101

- Percent change from baseline to visit 22 in peanut-specific IgE in subjects (continuously) treated with dupilumab plus AR101 vs subjects treated with placebo plus AR101
- Percent change from baseline to the end of study visit 25 in peanut-specific IgE in subjects (continuously) treated with dupilumab plus AR101 vs subjects treated with placebo plus AR101

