6.1. Definition of Baseline for Efficacy/Safety Variables

Unless otherwise specified, the study baseline assessment for all measurements will be the latest available valid measurement taken prior to the first administration of study drug. If any randomized subjects are not treated, the baseline will be the last value on or prior to the randomization. In addition, maintenance period baseline is defined as the last available valid measurement taken prior to the first administration of dupilumab/placebo during the maintenance period.

The following rules specify the determination of baseline by both date/time information:

- The date and time of first injection will be used to determine the baseline for the AE, lab, PK and ADA data.
- Only the date of first injection will be used to determine the baseline for other data expect AE, lab, PK and ADA data.

For the re-screened subjects, all data from the same subject will be used to derive baseline regardless if the data is from the screen-failure subject ID or enrolled subject ID.

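### The maintenance objectives compare visit 22 pass rates with placebo and no efficacy endpoint starts at visit 16, so children who lose desensitization cannot be told apart from those who gain it

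*SAP*

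**What the plan says.** SAP 1.2.2 has two maintenance objectives, one for continuous and one for limited dupilumab. Each asks whether dupilumab "compared to placebo maintains desensitization, defined as an increase in the proportion of subjects who pass a post maintenance DBPCFC at visit 22". Protocol 2.2 is worded the same way. Protocol 3.2.2 says of the design: "It will also evaluate the effect of dupilumab in maintaining the response to AR101".

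The matching endpoints in SAP 4.5.2 are of two kinds. One is a pass proportion at visit 22 ("Proportion of subjects (continuously) treated with dupilumab plus AR101 vs placebo plus AR101 who" pass the challenge, with a parallel endpoint for those switched to placebo). The other is a dose change from the study baseline: "Change in the cumulative tolerated dose (log transformed) of peanut protein during a DBPCFC from baseline to visit 22 in subjects (continuously) treated", again with a parallel endpoint for the switched arm. Each is set against placebo plus AR101.

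On the analysis set, SAP 3.1 states: "The FAS-maintenance is the primary analysis set for efficacy analyses at visit 22". Entry requires 300 mg/day for at least 2 weeks; a visit 16 pass is not required. SAP 5.6.2 analyses visit 22 by the visit 16 methods. SAP 5.6.3 sets no formal hypothesis and no multiplicity adjustment for maintenance, and Protocol 11.4.3.2 calls the visit 22 analyses descriptive, with optional tests.

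The SAP does use later start points elsewhere. SAP 1.2.3 adds "Change in the cumulative tolerated dose (log transformed) of peanut protein during a DBPCFC from visit 22 to visit 25" as an exploratory endpoint, and SAP 6.1 says the "maintenance period baseline is defined as the last available valid measurement taken prior to the first administration of dupilumab/placebo" during that period. SAP 5.7 uses a visit 16 baseline for safety summaries. No efficacy endpoint uses one.

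**The concern.** In ordinary use, maintaining desensitization means passing at visit 16 and still passing at visit 22. The visit 16 result enters none of the visit 22 endpoints. Two things follow.

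- The arms are planned to differ by 25 points at visit 16. A visit 22 gap can be that earlier gap carried forward, whatever happened during maintenance.
- The analysis set includes children who failed at visit 16. A new pass at visit 22 offsets a lost one, so the net rate hides both.

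The 24-week maintenance phase exists to show whether the response holds when dupilumab is continued or stopped. As worded, the objective can be met while passers are being lost, and missed with no losses if placebo catches up on AR101. At stake is what the clinical study report may fairly say about maintenance.

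**Working it through.** **The plan's own figure.** SAP 2.3 gives 80% power for 104 vs 52 at 65% vs 40%, two-sided Fisher exact test at 5%. Exact enumeration gives 81.1%, so the inputs reproduce. The documents give no sample size, power or margin for visit 22.

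**Inputs for the illustration**
- Visit 16 pass rates of 65% and 40%, with 104 and 52 randomised (SAP 2.3).
- 1:1 re-randomisation of the dupilumab arm (SAP 2.1): 104/2 = 52 per dupilumab maintenance arm before selection.
- Share reaching 300 mg/day: an assumption. SAP 1.1 cites up to 20% unable to complete up-dosing in oral immunotherapy generally, so 80% is used for each arm and then varied.

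**Starting point in FAS-maintenance**
- Subjects per arm: 52 × 0.8 = 41.6, about 42.
- Visit 16 passers: 52 × 0.65 = 33.8, about 34 of 42 (81%), in each dupilumab maintenance arm; 52 × 0.40 = 20.8, about 21 of 42 (50%), on placebo.

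**How much loss the visit 22 comparison tolerates if placebo keeps all 21**

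| Dupilumab arm at visit 22 | Net loss from 34 | Against placebo 21/42 | Fisher p |
|---|---|---|---|
| 31/42 (74%) | 3 | higher | 0.042 |
| 30/42 (71%) | 4 | higher | 0.073 |
| 27/42 (64%) | 7 | higher | 0.27 |
| 22/42 (52%) | 12 | higher | 1.0 |

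The numerical increase survives a net loss of 12/34 = 35%. Nominal significance survives a net loss of 3/34 = 9%. With 70% to 100% reaching 300 mg/day, the first limit stays at 12 and the second is 2 to 4.

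**One passer in five lost.** 0.65/0.8 = 81.25%; 81.25% × 0.8 = 65%, against 0.40/0.8 = 50%. The worded increase is met by 15 points. Exact enumeration of the 1-df CMH statistic (one stratum, 42 vs 42) gives nominal significance about 29% of the time.

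**No change at all during maintenance.** The same statistic at 81.25% vs 50% measures carry-over alone:

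| Share reaching 300 mg/day (dupilumab / placebo) | Nominally significant |
|---|---|
| 70% / 70% | 96% |
| 80% / 80% | 87% |
| 90% / 90% | 79% |
| 100% / 100% | 72% |
| 90% / 80% | 55% |
| 95% / 75% | 29% |

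The last two rows matter because the trial itself tests whether dupilumab raises this share.

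**What a within-subject summary would show.** Suppose 27 of 34 passers hold on dupilumab and 21 of 21 on placebo, with no new passes. Retention is 79% (exact 95% CI 62% to 91%) against 100% (84% to 100%), Fisher p=0.036 in favour of placebo. The planned comparison on the same children is 27/42 = 64% vs 21/42 = 50%, in favour of dupilumab (p=0.27).

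**Reading the two visits side by side.** At visit 16 the FAS rates are 65% and 40%. At visit 22, after a one-in-five loss on dupilumab and none on placebo, the FAS-maintenance rates are 65% and 50%. Dupilumab looks unchanged and placebo appears to improve, only because the denominator shrank.

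**The case against.** The documents define their term openly. For an adjunct, whether an advantage over AR101 alone persists at visit 22 is a legitimate question, and placebo catching up is a valid answer to it. That stands: the visit 22 comparisons should stay. It does not make them a measure of maintenance.

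A reader might infer that the planned output says nothing about change between the visits. That goes too far. Visit 16 is also analysed on the FAS, and only children at 300 mg/day for at least 2 weeks take that challenge, which is also the entry condition for FAS-maintenance. Apart from imputed values, the numerators correspond and the denominators differ in a known way. A careful reader could recover a crude net change for placebo and for the two dupilumab maintenance arms combined. A line plot of the visit 22 dose endpoints is also planned (SAP 10.1). What cannot be recovered is who lost and who gained.

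The continued and stopped arms come from re-randomisation and should start level, so excess loss after stopping would appear as a gap between them at visit 22. This also stands. However, the listed endpoints compare each arm with placebo, not with each other, and a loss common to both arms would not show in that contrast.

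Finally, these are secondary objectives in a phase 2 trial, without a formal hypothesis. The primary and the multiplicity-controlled endpoints are untouched.

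**Conclusion.** The concern holds. The stated definition of maintaining desensitization is a between-arm comparison at visit 22. It carries over the visit 16 difference and cannot separate losses from gains, and no efficacy endpoint fills the gap although a maintenance-period baseline is already defined. That structural point needs no assumptions.

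The size does. Under the planned visit 16 rates and 80% reaching 300 mg/day, a dupilumab arm can lose a net 12 of 34 passers and still show the worded increase, but only 3 of 34 and stay nominally significant if placebo is stable.

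Two stronger readings are not supported. A reader might take the 87% as the chance of wrongly claiming maintenance. It is the no-change case, in which desensitization was in fact maintained, and it ranges from 29% to 96% with the share reaching 300 mg/day. A reader might also infer that an arm losing one passer in five would probably be declared significantly better; if placebo is stable, that happens about 29% of the time. The consequence is limited to descriptive or nominal conclusions about maintenance.

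**What to change.** Keep the visit 22 comparisons with placebo, but report them as desensitization at visit 22. On the FAS-maintenance, by maintenance arm, pre-specify before database lock:

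1. The visit 16 by visit 22 pass/fail cross-table at 2044 mg, with the proportion of visit 16 passers who pass again at visit 22 and its exact 95% CI.
2. The change in log cumulative tolerated dose from visit 16 to visit 22, with the visit 16 value as covariate.

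Make continued vs stopped dupilumab the main contrast for both, since those arms were re-randomised. The schedule of events already places both visit 16 challenge days before the first maintenance injection, so the visit 16 result is a proper starting value. Label dupilumab vs placebo among passers as descriptive, because passing is an outcome that follows the initial randomisation.

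The cost is SAP wording and two tables from data already collected, with no change to conduct. The downside is precision: about 34 passers per dupilumab maintenance arm, where 27/34 has a 95% CI of 62% to 91%, in a subset selected after the initial randomisation.

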1.2.3. Modifications from the Statistical Section in the Final Protocol

Modifications from protocol amendment 4

- Added that the data will be summarized by treatment groups during pre-dosing period of AR101 (4 weeks) separately.
- Revised the secondary objective "To assess the effect of dupilumab (compared to placebo) as adjunct to AR101 on the change in peanut-specific IgE, IgG, IgG4, and peanut-specific IgG4/IgE ratio" as "To assess the effect of dupilumab (compared to placebo) as adjunct to AR101 on the change in peanut-specific IgE, IgG, IgG4, peanut-specific IgG4/IgE ratio and peanut-specific IgG/IgE ratio".
- Removed the last secondary objective "To assess if dupilumab increases the tolerability of AR101 as measured by the daily symptoms (e-diary) during the up-dosing phase" and corresponding secondary endpoints "Proportion of subjects experiencing allergic symptoms by treatment group during the up-dosing phase, mean severity score for each symptom by treatment during up-dosing phase, maximum severity score for each symptom by treatment during up-dosing phase, and difference in mean/median duration of symptoms by treatment group during up-dosing phase, and difference in mean/median duration of symptoms by treatment group during up-dosing phase (all endpoints measured by the daily symptom e-diary)" due to the low compliance of the allergy symptoms entry in eDiary. Instead, the following exploratory endpoints are added:
 - Proportion of days with one or more of any peanut allergy symptoms excluding food challenge test days during the updosing period up to visit 16
 - Proportion of days with one or more severe form of any peanut allergy symptoms (i.e. severity score of 7 or more) excluding food challenge test days during the updosing period up to visit 16

- Proportion of days with one or more symptoms for each symptom category excluding food challenge test days during the updosing period up to visit 16
- The following exploratory endpoints are added as well:
 - Change in the cumulative tolerated dose (log transformed) of peanut protein during a DBPCFC from visit 22 to visit 25
 - Proportion of subjects who "pass" a DBPCFC with 2044 mg (cumulative) peanut protein at visit 25
 - Change from baseline in total FAQLQ score at visit 16, visit 22 and visit 25 for different types of FAQLQ form
 - Proportion of subjects experiencing none, mild, moderate, severe or higher allergic symptoms by treatment group during DBPCFCs of peanut protein at visit 16, visit 22, and visit 25
 - Change and percent change from baseline to visit 16, visit 22 and visit 25 in peanutspecific IgG
 - Change and percent change from baseline to visit 16, visit 22, and visit 25 in peanutspecific IgG4
 - Change and percent change from baseline to visit 16, visit 22, and visit 25 in total IgE
 - Change from baseline to visit 16, visit 22, and visit 25 in log- transformed peanutspecific IgG4/ peanut-specific IgE ratio
 - Change from baseline to visit 16, visit 22, and visit 25 in log- transformed peanut-specific IgG/ peanut-specific IgE ratio
 - Change from baseline to visit 16, visit 22 and visit 25 in peanut-specific IgE
 - Change from baseline to visit 16, visit 22 and visit 25 in log- transformed peanutspecific IgE/total IgE ratio
 - Change and percent change from baseline to visit 16, visit 22 and visit 25 in Ara h1 sIgE, Ara h1 sIgG4, Ara h2 sIgE, Ara h2 sIgG4, Ara h3 sIgE, Ara h3 sIgG4
 - Change from baseline to visit 16, visit 22 and visit 25 in log- transformed Ara h1specific IgG4/ Ara h1-specific IgE ratio
 - Change from baseline to visit 16, visit 22 and visit 25 in log- transformed Ara h2-specific IgG4/ Ara h2-specific IgE ratio
 - Change from baseline to visit 16, visit 22 and visit 25 in log- transformed Ara h3-specific IgG4/ Ara h3-specific IgE ratio
 - Change from baseline to visit 16, visit 22 and visit 25 in Ara h1-specific IgE/ peanut-specific IgE ratio
 - Change from baseline to visit 16, visit 22 and visit 25 in Ara h2-specific IgE/ peanut-specific IgE ratio

- Change from baseline to visit 16, visit 22 and visit 25 in Ara h3-specific IgE/ peanut-specific IgE ratio
- Change and percent change from baseline to visit 16, visit 22 and visit 25 in basophil sensitivity to peanut allergen, as measured by EC50, which is the concentration of peanut protein required to achieve 50% of maximal basophil activation
- Change and percent change from baseline to visit 16, visit 22 and visit 25 in the frequency of peanut-specific T cell subsets (e.g. Th2A cell)

